2.3.2 Confirmatory Cohorts

For the Confirmatory Cohorts, enrollment will only start after the dosing of BRV is determined based on the PK findings of the Exploratory Cohort and an existing PK model from N01263. A total of at least 36 subjects without adequate seizure control after receiving one or more of the following AEDs prior to or at the time of enrollment: PB, MDZ, PHT, LEV (\leq 60mg/kg/day), or LDC (first-line, second-line, or subsequent treatment, which may have started prior to the subject's admission into the study site; dose and dosing regimen at the Investigator's discretion) will enter the Confirmatory Cohorts. The AED treatment can be continued if the subject is on a stable dose for at least 1 hour at the time the first BRV infusion is initiated.

Three consecutive Confirmatory Cohorts (n=12 each) are planned; each cohort must have at least 2 subjects undergoing hypothermia treatment. A PK and safety data review will be performed by the DMC after completion of each of the 3 Confirmatory Cohorts (12 subjects each), but no later than intervals of 6 months. During the PK and safety data review of data from the first and second Confirmatory Cohorts, the recruitment of subjects into subsequent cohorts will continue.

The study periods for the Confirmatory Cohorts are as follows:

- Screening Period: from signing and dating of the written ICF up to initiation of the first BRV dose.

The Screening Period starts up to 36 hours prior to the first administration of BRV. Phenobarbital, MDZ, PHT, LEV ($\leq 60\text{mg/kg/day}$), or LDC may have been administered prior to the subject's enrollment into the study and/or at a location other than the study site.
- Baseline Period (included in the Screening Period):
 - For subjects with **intermittent ENS**: at least 1 hour prior to entering the Evaluation Period.
 - For subjects in status epilepticus: up to 30 minutes prior to entering the Evaluation Period. At least 15 minutes of continuous seizures, or 50% of cumulative seizure activity during a 30-minute interval are to be confirmed on EEG before the administration of BRV can start.

As soon as subjects are considered to be in status epilepticus, steps required for the preparation of the initial BRV infusion can be initiated (eg, assignment of BRV kits through interactive response technology [IRT] and the dilution of BRV solution for iv infusion), even if the required EEG recording is not completed by that time.

Status epilepticus in neonates for the purpose of this study is defined as follows: 15 minutes of continuous or cumulative electrographic or electroclinical seizure within 30 minutes

The occurrence of ENS during the Baseline Period must be confirmed either by the local or central VEEG reader prior to BRV administration. Preferably, the central VEEG reader should confirm the required ENS. Video-EEGs that are acquired per standard of care prior to consenting and meet study-specific technical and quality requirements (eg, ability for immediate cloud-based central review) can be used as part of the Baseline assessment VEEG.
- Evaluation Period (96 hours): The first administration of BRV marks the starting point of the Evaluation Period. All subjects will receive iv BRV. The BRV dose for subjects in the Confirmatory Cohorts will be determined based on the results of the PK analysis of the Exploratory Cohort (predicted to be approximately the BRV plasma concentrations in the same range as those observed at the highest recommended dose in older children and adults who receive BRV 200mg/day). If subjects do not benefit from BRV treatment after 96 hours of BRV administration, BRV administration will be stopped and replaced by another AED.

Following the first BRV infusion, 6 PK blood microsamples (60 $\mu\text{L}/\text{sample}$) will be collected during the 96-hour Evaluation Period for each subject for the determination of plasma concentrations of BRV and its metabolites.

The AED PK sample should be collected 3 hours after the start of the initial BRV administration. In addition, opportunistic blood samples for the PK analysis may be used at the Investigator's discretion at any time during the Evaluation Period.

At the end of the Evaluation Period, subjects who benefit from BRV treatment may enter the BRV Extension Period in accordance with the Investigator's opinion. Subjects not entering the BRV Extension Period will proceed to the Down-Titration Period.

- BRV Extension Period (up to 28 days of postnatal age [+7 days]): Subjects can proceed to the BRV Extension Period if they benefit from BRV treatment during the Evaluation Period, in accordance with the Investigator's opinion. All subjects who participate in the BRV Extension Period must be offered entry into the long-term study, if they meet the eligibility criteria. Subjects will participate in the BRV Extension Period until they reach a stable condition that will allow them to enter the long-term study, if epilepsy is confirmed. The maximum anticipated duration of the BRV Extension Period per subject is up to 28 days of postnatal age (+7 days). Subjects must switch to BRV oral solution before entering the long-term study. The time point of the switch from iv to oral solution will be at the discretion of the Investigator.

Subjects who are not able to be dosed with BRV oral solution when they reach 28 days of postnatal age may continue in the BRV Extension Period for an additional 7 days; subjects who are not able to be switched to BRV oral solution by the end of the additional 7 days of the BRV Extension Period will not be eligible for enrollment in the long-term study.

During the BRV Extension Period, subjects may continue receiving the same BRV dose administered at the end of the Evaluation Period; the BRV dose should not be increased, but may be decreased at the discretion of the Investigator.

- Down-Titration Period (up to 1 week): A Down-Titration Period of up to 1 week is recommended for subjects in the Confirmatory Cohorts who discontinue BRV treatment prior to completion of the Evaluation Period, who do not proceed to the BRV Extension Period, or start the BRV Extension Period but do not enter the long-term study. The Down-Titration steps and duration may be adjusted at the Investigator's discretion.
- Safety Follow-Up Period: Subjects will proceed to the Safety Follow-Up Period once they complete the Down-Titration Period. The visit will occur 30 ± 3 days after the final administration of BRV.

Rescue medication should be given if the following occurs:

- There is no improvement in seizure burden within the first 3 hours after administration of BRV.
- Seizure burden is unacceptable to the Investigator, in which case rescue medication can be given earlier at any time, but ideally not in the first 3 hours after the initial administration of BRV.

Subjects in the Confirmatory Cohorts are allowed to switch over from BRV to another AED (eg, MDZ or PHT), if needed. Subjects discontinuing BRV treatment during the Evaluation Period should start the Down-Titration Period while completing the Evaluation Period in parallel for the full 96 hours. In this case, subjects will complete all study assessments, except the collection of

blood microsamples for the determination of BRV plasma concentrations. Ideally, changing or adding a new treatment should not occur during the first 3 hours after the initial administration of BRV. Subjects who are switched from BRV to another AED will not be eligible to participate either in the BRV Extension Period or the long-term study.

2.3.3 Study duration per subject

The maximum study duration per subject will be up to 75 days (Screening Period [including Baseline Period (Confirmatory Cohorts only)], Evaluation Period, BRV Extension Period, Down-Titration Period [Confirmatory Cohorts only], and Safety Follow-Up Period). The individual study duration will be shorter depending on the type of cohort to which subjects will be assigned, the age at enrollment, and the decision to enter the BRV Extension Period.

The maximum BRV exposure per subject will be up to 42 days, which comprises up to 4 days during the Evaluation Period (depending on type of cohort), up to 28 days (+7 days) of postnatal age during the BRV Extension Period, and up to 1 week during the Down-Titration Period for subjects in the Confirmatory Cohorts only.

All subjects who do not continue into the long-term study will proceed to the Safety Follow-Up Period, and a visit will occur 30 ± 3 days after the final dose of BRV.

The end of the study is defined as the date of the last visit of the last subject in the study.

2.4 Determination of sample size

At least 42 evaluable subjects will be enrolled in this study, with at least 6 subjects in the Exploratory Cohort and at least 36 subjects will be enrolled in 3 successive Confirmatory Cohorts, each consisting of 12 subjects. At least 2 subjects undergoing hypothermia treatment will be included in the Exploratory Cohort and each of the 3 Confirmatory Cohorts.

Subjects in the Exploratory Cohort might be replaced due to lack of data, as deemed necessary following the review of PK and safety data by the DMC.

No formal sample size calculation has been performed as a single treatment BRV arm is planned for descriptive summary results and for comparison with the 6 subjects from the Exploratory Cohort. The total number of at least 36 subjects in the Confirmatory Cohorts is expected to provide sufficient evidence of tolerability, safety, and efficacy, as well as good precision for the PK profile of BRV in neonates.

Confirmatory Cohort subjects who drop out or are withdrawn from study participation will not be replaced.

3 DATA ANALYSIS CONSIDERATIONS

3.1 General presentation of summaries and analyses

Statistical analysis and generation of tables, figures, subject data listings, and statistical output will be carried out using SAS® Version 9.3 or higher.

Descriptive statistics, such as the number of subjects with available measurement (n), mean, standard deviation (SD), median, minimum value, and maximum value for quantitative variables, and counts and percentages for categorical variables, will be provided. Confidence intervals (95% CIs) will be provided for efficacy variables.

Unless otherwise noted, denominator for percentages will generally be based on the set of subjects with at least 1 assessment at the time point or at least 1 assessment during the time interval being summarized.

Decimal places for descriptive statistics will always apply the following rules:

- “n” will be an integer.
- Mean, SD and median will use 1 additional decimal place compared to the original data.
- Minimum and maximum will have the same number of decimal places as the original value.

Unless otherwise noted, all percentages will be displayed to 1 decimal place. No percentage will be displayed for zero counts, and no decimal will be presented when the percentage is 100%.

In general, descriptive summaries will be used to present study results overall (for the Confirmatory Cohorts) and by cohorts (Exploratory Cohort and each individual Confirmatory Cohort).

Subject data listings will be provided and will present source data and key derived variables for statistical analyses.

3.2 General study level definitions

3.2.1 Analysis time points

3.2.1.1 Relative day and time

For measurements with date and time collected, relative day and time will be calculated.

Relative day and time in 24-h clock will be calculated as current date minus first dose date, current time in hours minus first dose time in hours, current time in minutes minus first dose time in minutes (add 1 minute if the current date and time is the same or after the first dose date and time).

The relative time will be displayed in hours and minutes for relative times \leq 24 hours before or after the first BRV administration. For relative times $>$ 24 hours the relative day and time will be calculated in days, hours and minutes. If the current date and time is the same as the first dose date and time, the relative time is 1 minute. If the current date and time is prior to the first dose date and time, then the relative day and time will be denoted by “-”. If the current date and time is after the last dose date the relative day and time will be displayed with a leading “+”.

The relative day and time in the tables and listings will be displayed in days, hours and minutes where applicable.

- Example 1: first dose date and time is 5-Jan-2017: 10:30 am. The current date and time is 5-Jan-2017: 8:45 am. The relative day and time is calculated as 5-Jan-2017 minus 5-Jan-2017=0, 8:00 h – 10:00 h= -2:00 h, 45 min-30 min=15 min. The relative day and time is 0 d 1 h 45 min and will be displayed as -1 h 45 min.
- Example 2: first dose date and time is 5-Jan-2017: 10:30: am. The current date and time is 7-Jan-2017: 8:45 am. The relative day and time is calculated as 7-Jan-2017 minus 5-Jan-2017=2 d (48 h), 8:00 h – 10:00 h= -2:00 h, 45 min-30 min + 1 min=16 min. The relative day and time is 1 d 22 h 16 min.

- Example 3: first dose date and time is 5-Jan-2017: 10:30 am. The current date and time is 3-Jan-2017: 8:45 am. The relative day and time is calculated as 3-Jan-2017 minus 5-Jan-2017 = -2 d (-48 h), 8:00 h – 10:00 h = -2:00 h, 45 min-30 min=15 min. The relative day and time is -2 d 1 h 45 min.

Relative day and time will not be calculated for partial dates and times.

3.2.1.2 Relative day

For measurements with only date collected, relative day will be calculated. Relative day will be calculated as the date of first dose of study medication minus the current date for days prior to the first dose of study medication. During treatment (from the day of first study medication dose until the day of last study medication dose), relative day will be calculated as the current date minus the date of first dose of study medication plus 1 (eg, the day of first dose will be Day 1 and the day prior to first dose will be Day -1). For days after the last dose of study medication, relative day will be calculated as the current date minus the date of last study medication dose and will include a '+' to denote post-treatment days (eg, the day after the last dose will be Day +1). Relative day will not be calculated for partial dates.

3.2.2 Study periods for analysis

3.2.2.1 Exploratory cohort study periods

3.2.2.1.1 Screening Period

The Screening Period will start on the date of the written informed consent form (ICF) and will end immediately prior to initiating the first BRV dose. The Screening Period starts up to 36 hours prior to the first administration of BRV.

3.2.2.1.2 Evaluation Period

Evaluation Period starts with the first BRV initiation and will end 48 hours after first BRV initiation.

3.2.2.1.3 BRV Extension Period

If it is decided that the subject continues BRV administration after the Evaluation Period, the Extension Period starts after the end of the Evaluation Period. Subjects who will not attend the long term follow-up study, will have no Extension Period.

If the subject will be enrolled in the long term follow up study, the end of the Extension Period is defined as last contact during N01349. In this case the maximum duration of the period will be 35 days.

In case subject attends the Extension Period but then it's decided to stop the BRV administration, the subject will continue with the Safety Follow-up Period and the end of the Extension Period will be defined as the date and time of last BRV administration.

Subjects not entering the BRV Extension Period will proceed immediately to the Safety Follow-Up Period.

The BRV Extension Period may consist of Extension Period Visit 1 (EPV1), Extension Period Visit 2 (EPV2), Unscheduled Visit and Telephone Contact.

3.2.2.1.4 Safety Follow-Up Period

Subjects will proceed to the Safety Follow-Up Period if they do not require further BRV administration. The start of the Safety Follow-up Period will be defined as after the end of the last BRV administration. The end of the Safety Follow-up Period will be defined as last contact to the subject, which will be the Follow-Up visit. This visit will occur 30 ± 3 days after the final administration of BRV.

3.2.2.2 Confirmatory Cohorts study periods

3.2.2.2.1 Screening Period

The Screening Period will start on the date of the written ICF and will end prior to initiating the first BRV dose. Screening Period includes Baseline Period described below.

3.2.2.2.2 Baseline Period

Baseline Period (-1h to 0h) begins 1 hour before and ends immediately prior to the first initiation of BRV infusion. The Baseline Period is included in the Screening Period.

3.2.2.2.3 Evaluation Period

Evaluation Period starts when the subject receives first dose of BRV infusion and will last for 96 hours. If subjects do not benefit from BRV treatment after 96 hours of BRV administration, BRV administration will be stopped and replaced by another AED; however, the subject's participation in the study will continue.

3.2.2.2.4 BRV Extension Period

BRV Extension Period starts after the end of the Evaluation Period, subjects who benefit from BRV treatment may enter the BRV Extension Period in accordance with the Investigator's opinion.

If the subject will be enrolled in the long term follow up study, the end of the Extension Period is defined as last contact during N01349. In this case the maximum duration of the period will be 35 days.

In case subject attends the Extension Period but then it's decided to not continue the BRV administration, the subject will continue with the Down Titration Period and the end of the Extension Period will be defined as the date and time of last stable dose of BRV infusion.

Subjects not entering the BRV Extension Period will proceed immediately to the Down-Titration Period.

The BRV Extension Period may consist of Extension Period Visit 1 (EPV1), Extension Period Visit 2 (EPV2), Unscheduled Visit and Telephone Contact.

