Rescue medication should be given if the following occurs:

- There is no improvement in seizure burden within the first 3 hours after administration of BRV.
- Seizure burden is unacceptable to the Investigator, in which case rescue medication can be given earlier at any time, but ideally not in the first 3 hours after the initial administration of BRV.

Subjects in the Confirmatory Cohorts are allowed to switch over from BRV to another AED (eg, MDZ or PHT), if needed. Subjects discontinuing BRV treatment during the Evaluation Period should start the Down-Titration Period while completing the Evaluation Period in parallel for the full 96 hours. In this case, subjects will complete all study assessments, except the collection of blood microsamples for the determination of BRV plasma concentrations. Ideally, changing or adding a new treatment should not occur during the first 3 hours after the initial administration of BRV. Subjects who are switched from BRV to another AED will not be eligible to participate either in the BRV Extension Period or the long-term study.

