7.2 Treatments to be administered

Subjects in the Exploratory Cohort will be dosed during the Evaluation Period with BRV (0.5mg/kg bid) according to the sites standard procedures. Treatment with AEDs per SOC (first-line, second-line, or subsequent treatment) will continue in parallel with BRV treatment.

For subjects who enter the Confirmatory Cohorts, the dosing of BRV (1mg/kg bid [2mg/kg/day]) has been determined based on the PK findings of the Exploratory Cohort. The DMC will continue to monitor the PK and safety of the subjects and dosing may be adjusted as new data are available. Administration of BRV is proposed as approximately 15-minute iv infusions.

Treatment with previous AEDs (PB, MDZ, PHT, LEV [\leq 60mg/kg/day], or LDC) during the Evaluation Period is permitted to continue if the subject is on a stable dose from 1 hour prior to initiation of the BRV treatment.

Subjects can switch from iv to oral BRV at any time during the BRV Extension Period.

For subjects who are switched to BRV oral solution, the dose will be measured using the appropriate syringes (1mL, 3mL or 10mL) with an adaptor able to fit all the bottle sizes. Oral solution should not be mixed with other liquids prior to administration.

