3.2.2.2.5 Down Titration Period

Down-Titration Period will start after the Evaluation Period or after the BRV Extension Period, can last up to 1 week. The end of the Down-Titration period is defined as day and time of last BRV administration.

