10.2.1 General summaries of AEs

A table with overall summary of AEs will be provided separately for Evaluation Period, Extension Period, Down-Titration Period, Safety Follow-up Period and for the entire study, the table will include:

- the numbers and percentages of subjects with at least one TEAE
- the number and percentage of subjects with serious TEAEs
- the number and percentage of subjects with non-serious TEAEs
- the number and percentage of subjects with a TEAE that led to permanent discontinuation of study medication
- the number and percentage of subjects with a drug-related TEAE
- the number and percentage of subjects with a drug-related serious TEAE
- the number and percentage of subjects with a severe TEAE
- the number and percentage of subjects with AE leading to death
- the number and percentage of subjects with TEAEs leading to death
- the number and percentage of subjects who died prior to the first BRV dose

The following summary tables of AEs/TEAEs will be provided by primary SOC and PT. Summaries will be presented by Exploratory Cohort and individual Confirmatory Cohorts and for overall combined Confirmatory Cohorts for the SS.

- Incidence of pre-treatment AEs

Pre-treatment AEs are defined as AEs that had onset strictly prior to the date/time of the first dose of BRV

- Incidence of TEAEs (for Evaluation Period, Extension Period, Down-Titration Period, Safety Follow-up Period and for the entire study)
- Incidence of serious TEAEs
- Incidence of non-serious TEAEs

- Incidence of TEAEs by maximum intensity
Each subject will be counted at most once per primary SOC or PT according to the maximum intensity of all AEs within that SOC or PT. Severe intensity will be assumed for AEs for which intensity is not specified.
- Incidence of drug-related TEAEs
Drug-related AEs are AEs for which the relationship to study medication is specified by the Investigator as Related or AEs for which relationship is not specified.
- Incidence of drug-related serious TEAEs
Drug-related AEs are AEs for which the relationship to study medication is specified by the Investigator as Related or AEs for which relationship is not specified.
- Incidence of TEAEs by relationship
- Incidence of non-serious TEAEs by relationship
- Incidence of serious TEAEs by relationship
- Incidence of fatal TEAEs by relationship
- Incidence of TEAEs leading to permanent discontinuation of study medication
- Incidence of TEAEs leading to death

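### SAP period boundaries for the Confirmatory Cohorts put AEs on stable oral BRV outside the Extension table and keep AEs in tapers run before hour 96 out of the withdrawal summaries

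*SAP*

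**What the plan says.** **End of the Confirmatory Extension.** SAP 3.2.2.2.4 gives two rules. For a subject who rolls over to the long-term study, "the end of the Extension Period is defined as last contact during N01349". For a subject who enters the Extension and then stops BRV, "the end of the Extension Period will be defined as the date and time of last stable dose of BRV infusion".

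**Down-Titration.** SAP 3.2.2.2.5 states: "Down-Titration Period will start after the Evaluation Period or after the BRV Extension Period, can last up to 1 week". It adds: "The end of the Down-Titration period is defined as day and time of last BRV administration".

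**Oral dosing.** Protocol 7.2 states: "Subjects can switch from iv to oral BRV at any time during the BRV Extension Period". Protocol 8.2.3 allows oral treatment at home.

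**Early stopping.** Under Protocol 5.1.2, subjects who discontinue BRV during Evaluation "should start the Down-Titration Period while completing the Evaluation Period in parallel for the full 96 hours". SAP 2.3.2 repeats this rule. SAP 3.2.2.2.3 fixes Evaluation at 96 hours from the first infusion.

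**Use of the periods.** SAP 10.2.1 lists "Incidence of TEAEs (for Evaluation Period, Extension Period, Down-Titration Period, Safety Follow-up Period and for the entire study". SAP 10.4.11 builds its named withdrawal and rebound summaries, and the listing, from AEs with onset in the Down-Titration Period.

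**Exploratory Cohort.** SAP 3.2.2.1.3 says: "Subjects who will not attend the long term follow-up study, will have no Extension Period". The same section then defines when the Extension ends for a subject who enters it and later stops BRV.

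**The concern.** AEs are the secondary safety variable, and the period tables are where a reader looks to see whether events cluster on maintenance treatment or on stopping. Two boundary rules do not match how BRV is given and stopped in this study. One refers only to infusions in a period when subjects may be on oral solution. The other leaves no room for a taper that the design text places inside the 96-hour Evaluation Period.

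The withdrawal and rebound summaries are the most exposed, because they select on Down-Titration onset. They could take in events from stable oral dosing, and they would omit events from tapers that run during Evaluation, which belong to the stopping phase they are meant to examine. With at least 36 Confirmatory subjects planned, and only some of them tapering, a few misplaced events could change what those summaries show.

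**Working it through.** The plan states no figure on this point, so there is none to reproduce. The check applies the SAP rules literally to example timelines. **All dates are assumed**; the documents give none for the switch to oral or for tapering.

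**1. Oral dosing after the last infusion (Confirmatory subject who stops without rolling over)**

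Inputs from the documents: Evaluation lasts 96 hours = 4 days (SAP 3.2.2.2.3); a taper lasts up to 7 days (SAP 3.2.2.2.5); the Extension is planned to PNA 28 (+7) days, or up to 90 days if the long-term study is unavailable (Protocol 5.1.2).

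Formulas, with the stated end of Down-Titration (last BRV administration) governing:
- SAP Down-Titration length = end of taper − last infusion
- stable oral days inside it = start of taper − last infusion
- share = stable oral days ÷ SAP Down-Titration length

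| Assumed PNA days | SAP Down-Titration | Stable oral inside it | Share |
|---|---|---|---|
| last infusion 26, stable oral to 28, 7-day taper | 35 − 26 = 9 | 28 − 26 = 2 | 2/9 = 22% |
| last infusion 10, stable oral to 28, 7-day taper | 35 − 10 = 25 | 28 − 10 = 18 | 18/25 = 72% |
| last infusion 10, stable oral to 90, 7-day taper | 97 − 10 = 87 | 90 − 10 = 80 | 80/87 = 92% |

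Each window is longer than one week, so the two halves of SAP 3.2.2.2.5 conflict. If the last administration governs, the stable oral AEs are Down-Titration AEs. If one week is a hard cap, those more than 7 days after the last infusion have no defined period. In neither case do they appear in the Extension table.

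SAP 5.1 also has a disposition category for subjects who switch to oral before the Extension. Take a first dose on day 2, so that Evaluation ends on day 6, and a last infusion on day 5.5. The Extension length is then 5.5 − 6 = −0.5 day: it ends before it begins.

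**2. Taper in parallel with Evaluation**

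Taper hours outside Down-Titration = min(96, end of taper) − hour of stopping. Taper hours inside = max(0, end of taper − 96).

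| Stable BRV stopped | Taper length | Taper ends | Outside | Inside |
|---|---|---|---|---|
| hour 24 | 72 h | hour 96 | 72 | 0 |
| hour 24 | 168 h | hour 192 | 72 | 96 |
| hour 12 | 48 h | hour 60 | 48 | 0 |

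In the last row the defined end of Down-Titration (hour 60) precedes its earliest start (hour 96), a length of 60 − 96 = −36 hours.

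**3. Exploratory Extension**

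Within SAP 3.2.2.1.3, one sentence denies an Extension Period to anyone not attending the long-term study, and another gives its end for a subject who enters it, stops BRV and moves to Safety Follow-Up. Both cannot be applied to the same subject.

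**4. After the fix, same assumed dates**

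First dose day 2, last infusion day 10, stable oral to day 28, 7-day taper: Extension 28 − 6 = 22 days and Down-Titration 7 days, against 10 − 6 = 4 and 25 days under the literal rule. Stop at hour 24 with a 72-hour taper: Down-Titration 72 hours, against 0.

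**The case against.** The strongest reply is that the reference to infusion in SAP 3.2.2.2.4 is a slip. SAP 7.1, 7.2 and 10.1 all treat oral BRV as Extension treatment, covering accountability, compliance and exposure. That is probably what was meant, but a programmer implements the written rule, and the slip leaves this section at odds with the others. The point stands.

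A reader might go further in four ways that the documents do not support.

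- *Parallel-taper AEs are lost from the safety analysis.* They are not. They are counted in the Evaluation and entire-study TEAE tables and in the listing of all AEs, and taper AEs after hour 96 are captured under Down-Titration. SAP 10.4.11 also says in general terms that withdrawal-related AEs will be used. Its named summaries, however, select on Down-Titration onset, and the omission is there.
- *The Down-Titration tables will consist mostly of maintenance oral dosing.* That holds only for long oral phases. A two-day oral phase gives 22%. The 92% case needs a subject kept on to PNA 90 days who then does not enter the long-term study; Protocol 5.1.3 allows this, but it is the extreme.
- *Exploratory AEs between 48 hours and the last dose belong to no period.* This takes one sentence of SAP 3.2.2.1.3 alone and ignores the later one that defines the end. It is a minor internal contradiction, in a cohort planned at 6 or more subjects.
- *The two cohorts should share one Extension end.* The difference is largely by design. The Exploratory Cohort has no Down-Titration Period, so its Extension naturally ends at the last administration, whereas the Confirmatory Cohorts need a boundary at the last stable dose.

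**Conclusion.** The point holds as a conflict between stated rules. As written, SAP 3.2.2.2.4 and 3.2.2.2.5 misallocate AEs by period for two groups of Confirmatory subjects: those who switch to oral BRV in the Extension and then stop without rolling over, and those who stop BRV during Evaluation and taper before hour 96. The damage is confined to the period-specific TEAE tables and the withdrawal and rebound summaries. Entire-study TEAE totals do not change, rollover subjects are unaffected because their Extension ends at last contact, and all analyses are descriptive.

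The number of subjects in either group cannot be derived from the documents. The 22% to 92% range and the hour counts rest on assumed switch, stop and taper dates, and the percentages also assume that the one-week limit is not a cap. The wording should be corrected before the period tables are programmed.

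**What to change.** Change SAP wording only; no dose or clinical rule is affected.

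- **SAP 3.2.2.2.4:** for subjects who stop BRV, end the Confirmatory Extension at the last stable BRV dose by any route (iv or oral) before the taper that follows the decision to stop. If there is no taper, end it at the last BRV administration. This second clause is needed because Down-Titration is only recommended (Protocol 5.1.2).
- **SAP 3.2.2.2.5:** start Down-Titration at the first taper dose after the decision to stop BRV, including before hour 96. State that a dose decrease permitted during the Extension (Protocol 5.1.2 and 8.2.3) does not start it.
- **SAP 10.2.1 and 10.4.11:** include TEAEs with onset in a parallel taper in the Down-Titration and withdrawal summaries as well as in the Evaluation table, and say that they appear in both.
- **SAP 3.2.2.1.3:** delete the sentence denying an Extension Period to subjects who do not attend the long-term study, or reconcile it with the rule for subjects who enter it and then stop.

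The cost is a short SAP amendment and the matching period derivation. One check is needed first. Protocol 7.7 requires dates and times for each iv dose, but home oral dosing relies on a diary and on an oral-solution CRF whose per-dose content is not described. Confirm that the data identify the decision to stop and the first taper dose.
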